### 5.2. Secondary *Efficacy* Objectives

- *To assess percent change from baseline to Week 12 in LDL-C*

[figure not shown]
### 5.3. Tertiary *Efficacy* Objectives

- *To assess percent change from baseline to Week 24 and to Week 52 in LDL-C in patients who do not receive adjunctive lipid-lowering therapy*
- *To assess high-density lipoprotein cholesterol (HDL-C), non-HDL-C, total cholesterol (TC), and TG at Weeks 12, 24, and 52*
- *To assess apoB and high-sensitivity C-reactive protein (hs-CRP) at Weeks 12, 24, and 52*

## 6. INVESTIGATIONAL PLAN

### 6.1. Overall Study Design

This is a Phase 3, randomized, double-blind, placebo-controlled, parallel group, study evaluating the long-term safety and tolerability of ETC-1002 in high CV risk patients with hyperlipidemia (patients with underlying HeFH and/or ASCVD) who are not adequately treated with their maximally tolerated lipid-modifying therapy. Maximally tolerated lipid-lowering therapy includes a maximally tolerated statin alone or in combination with other lipid-lowering therapies (eg, ezetimibe, fibrates [except gemfibrozil]). A patient's maximally tolerated lipid-modifying therapy will be determined by the investigator using their medical judgment and available sources, including the patient's self-reported history of lipid-modifying therapy.

The study will be conducted at approximately 125 clinical sites in United States, Canada, Germany, Netherlands, Poland, and United Kingdom.

Screening (Visit S1) will occur approximately 2 weeks prior to Day 1 (Visit T1). Patients on maximally tolerated lipid-lowering therapy, as determined by the investigator, will be stratified based on CV risk (HeFH and ASCVD diagnosis) and baseline statin dose category (see [Table 2](#)). Patients will be randomized into 1 of the 6 strata (see [Table 3](#)).

Statin dose categories, *based on average daily dose*, and randomization strata are defined in the [Table 2](#) and [Table 3](#) below, respectively:

**Table 2: Baseline Statin Dose Categories**

High Intensity Statins	Moderate Intensity Statins	Low Intensity Statins a
Atorvastatin 40-80 mg	Atorvastatin 10-20 mg	Simvastatin 10 mg
Rosuvastatin 20-40 mg	Rosuvastatin 5-10 mg	Pravastatin 10-20 mg
	Simvastatin 20-40 b mg	Lovastatin 20 mg
	Pravastatin 40-80 mg	Fluvastatin 20-40 mg
	Lovastatin 40 mg	Pitavastatin 1 mg
	Fluvastatin XL 80 mg	
	Fluvastatin 40 mg BID	
	Pitavastatin 2-4 mg	

a Low intensity statins also include those patients taking low-dose statins using an alternate regimen (ie, every other day, or for a specified number of times per week)

**Table 3: Randomization Strata**

HeFH (with or without ASCVD)	ASCVD (without HeFH)
HeFH+ Low Intensity Statins	ASCVD + Low Intensity Statins
HeFH+ Moderate Intensity Statins	ASCVD + Moderate Intensity Statins
HeFH+ High Intensity Statins a	ASCVD + High Intensity Statins a

ASCVD = Atherosclerotic cardiovascular diseases; HeFH = Heterozygous familial hypercholesterolemia.

[figure not shown]
a Simvastatin with doses  $\geq 40$  mg/day are not allowed in this study.

There will be no cap placed on randomization into any particular stratum. Randomized patients will return for clinic visits at Week 4 (Visit T2), Week 8 (Visit T3), Week 12 (Visit T4), Week 24 (Visit T5), Week 36 (Visit T6), and Week 52 (Visit T7). Patients who withdraw from investigational medicinal product (IMP) treatment will be asked to continue to be followed for safety using the protocol-specified visit schedule.

For details of study assessments, see the Schedule of Events in [Appendix 1](#).

An independent expert Data Monitoring Committee (DMC) will formally review accumulating unblinded safety *and* efficacy data from this and other ongoing studies of ETC-1002. All *clinical endpoints*, including *all major cardiac events (MACE) and non-MACE endpoints defined as: CV death (MACE), non-CV death (non-MACE), nonfatal myocardial infarction (MI) (MACE), nonfatal stroke (MACE), hospitalization for unstable angina (MACE), coronary revascularization (MACE), non-coronary arterial revascularization (non-MACE), and hospitalization for heart failure (non-MACE)*, will be adjudicated by an independent blinded expert Clinical Events Committee (CEC), using standardized definitions. *Any clinical endpoints that meet SAE criteria will be reported as SAEs*

**Figure 1. Study 1002-040 Study Design**

## 6.2. Study Hypothesis

The primary clinical hypothesis is that long-term exposure of ETC-1002 will be safe and well tolerated in high CV risk patients with hyperlipidemia (patients with underlying HeFH *and/or* ASCVD) who are not adequately controlled with their maximally tolerated lipid-modifying therapy, including a maximally tolerated statin.

The study will characterize the long-term safety and tolerability of ETC-1002 versus placebo in addition to maximally tolerated lipid-lowering therapy, including a maximally tolerated statin *alone or in combination with other lipid-lowering therapies*, in patients with hyperlipidemia. The randomized, double-blind, placebo controlled add-on to maximally tolerated lipid-lowering therapy design will ensure that long-term safety data are meaningful and interpretable. The extended treatment duration (52 weeks) and large patient number (n = 1950) will provide robust long-term safety in high CV risk patients who have an unmet medical need for additional lipid-lowering therapy, such as ETC-1002 once daily, orally bioavailable option.

## 6.3. Study Duration and Period

The expected total duration of study participation for each randomized patient is approximately 54 weeks. This duration includes a 2-week screening period and a 52-week treatment period.

#### **6.4. End of Study**

The study will end when the last randomized patient completes *their last study visit* (last patient last visit [LPLV] for last randomized patient). The estimated overall duration of the study (first patient first visit [FPFV] to LPLV) is approximately 28 months.

#### **6.5. Number of Patients**

The study will enroll approximately 1950 adult male and female HeFH and/or ASCVD patients with hyperlipidemia from approximately 125 clinical sites.

#### **6.6. Patient Identification Numbers**

A unique patient identification number will be assigned to each patient to identify each patient throughout the study and will be entered on all documentation. If a patient is not eligible to receive treatment, or if a patient discontinues from the study, their patient identification number cannot be assigned to another patient.

Patient identification numbers will be assigned sequentially by interactive web response system (IWRS) at the time of informed consent during the screening module transaction. The patient numbers will be an 8-digit patient unique number that is comprised of protocol, site, and patient-specific numbers (ie, 40-001-001 identifies Protocol 40, Site 001, Patient 001).

##### **6.6.1. Screening**

Screening will occur approximately 2 weeks prior to Day 1 (Visit T1) where the patient's eligibility will be evaluated. Eligible patients who are taking concomitant medications must be on stable regimens as defined in [Section 8.2](#). At the investigator's discretion, screening may be extended by 2 weeks to allow for re-evaluation of LDL-C, TG, blood pressure, liver enzymes, and estimated glomerular filtration rate (eGFR) eligibility criteria (see [Section 7.1](#) and [Section 7.2](#)).

##### **6.6.2. Randomization and Treatment Period**

For patients who satisfy all entry criteria and complete the 2-week screening period, randomization will occur and their randomization number will be assigned via IWRS at Week 0 (Visit T1). Patients will be stratified on CV risk (HeFH and ASCVD diagnosis) and baseline statin dose and randomized in a ratio of 2:1 to receive 1 of the 2 following treatments in a double-blind fashion:

- ETC-1002 180-mg tablet
- Matching placebo tablet
- For details regarding the randomization strata see [Table 3](#).

## 7. SELECTION AND WITHDRAWAL OF PATIENTS

### 7.1. Subject Inclusion Criteria

Each patient with hyperlipidemia must meet the following criteria to be randomized in this study:

1. Age  $\geq 18$  years or legal age of majority based on regional law, whichever is greater at Week -2 (Visit S1)
2. Men and nonpregnant, nonlactating women. Women must be either:
  - Naturally postmenopausal (as reported by the patient, defined as greater than 55 years and  $\geq 1$  year without menses, less than 55 years and  $\geq 1$  year without menses with follicle-stimulating hormone (FSH)  $\geq 40.0$  IU/L), or surgically sterile including hysterectomy, bilateral oophorectomy, or tubal ligation or;
  - Women of childbearing potential must be willing to use 1 acceptable method of birth control. *The minimal requirement for adequate contraception is that it should be started on Day 1, continuing during the study period, and for at least 30 days after the last dose of study drug.* Acceptable methods of birth control include: oral birth control medications; placement of an intrauterine device (IUD) with or without hormones; barrier methods including condom or occlusive cap with spermicidal foam or spermicidal jelly; vasectomized male partner who is the sole partner for this patient; or true abstinence (not including periodic abstinence such as calendar, ovulation, symptothermal, postovulation methods, or withdrawal).
  - There are no protocol-specific birth control requirements for men with partners who are able to become pregnant.
3. Fasting LDL-C value at Week -2 (Visit S1)  $\geq 70$  mg/dL (1.8 mmol/L).  
Note: LDL-C may be repeated 1 time with the screening period extended up to 2 weeks. For those patients who have a repeat LDL-C, the mean of the first value and the repeat value will be used to determine eligibility.
4. Have high cardiovascular risk that is defined as either:
  - Diagnosis of HeFH. Diagnosis must be made by either genotyping or by clinical assessment using either the World Health Organization (WHO) criteria/Dutch Lipid Clinical Network Criteria with a score that is  $>8$  points (see [Appendix 4](#)) or the Simon Broome Register Diagnostic Criteria with an assessment of 'Definite HeFH' (see [Appendix 5](#)). Patients with a diagnosis of HeFH may or may not have established CHD or CHD risk equivalents.

**OR**

- Have ASCVD (with established CHD or CHD risk equivalents)  
Documented history of CHD (includes 1 or more of the following):
  - Acute MI
  - Silent MI
  - Unstable angina
  - Coronary revascularization procedure (eg, percutaneous coronary intervention [PCI] or coronary artery bypass graft [CABG] surgery)
  - Clinically significant CHD diagnosed by invasive or non-invasive testing (such as coronary angiography, stress test using treadmill, stress echocardiography or nuclear imaging)

Documented CHD risk equivalents (includes 1 or more of the following criteria):

- Peripheral arterial disease
- Previous ischemic stroke with a focal ischemic neurological deficit that persisted more than 24 hours, considered as being of atherothrombotic origin. Computed tomography (CT) or magnetic resonance imaging (MRI) must have been performed to rule out hemorrhage and non-ischemic neurological disease

Note: Patients with T2DM are allowed in this study; however, for this study T2DM is not considered a CHD risk equivalent

5. Be on maximally tolerated lipid-modifying therapy, including a maximally tolerated statin *either alone or in combination with other lipid-lowering therapies*, at stable doses for at least 4 weeks prior to screening (6 weeks for fibrates; however, gemfibrozil is not allowed). Regimens other than daily dosing, including those at very low doses, are acceptable.

A patient's maximally tolerated lipid-modifying therapy will be determined by the investigator using their medical judgment and available sources, including the patient's self-reported history of lipid-modifying therapy.

## 7.2. Subject Exclusion Criteria

Patients who meet any of the following criteria will not be randomized:

1. Total fasting triglyceride  $\geq 500 \text{ mg/dL}$  ( $5.6 \text{ mmol/L}$ ) at Week -2 (Visit S1)

Note: TG may be repeated 1 time with the screening period extended up to 2 weeks. For those patients who have a repeat TG, the mean of the first value and the repeat value will be used to determine eligibility.

2. Renal dysfunction or nephritic syndrome or a history of nephritis, including eGFR (using central laboratory determined Modification of Diet in Renal Disease [MDRD] formula)  $<30 \text{ mL/min}/1.73 \text{ m}^2$  at Week -2 (Visit S1) [1].

Note: At the discretion of the investigator, the screening period may be extended up to 2 weeks for a single repeat eGFR. For those patients who have a repeat eGFR, the repeat value will be used to determine eligibility.

*Note: Also excluded are renally impaired patients receiving an average daily dose of simvastatin 40 mg with eGFR below  $<45 \text{ mL/min}/1.73 \text{ m}^2$ .*

3. Body mass index (BMI)  $\geq 50 \text{ kg}/\text{m}^2$
4. Concomitant use of simvastatin *at average daily doses greater than 40 mg.*
5. *Concomitant use of a PCSK inhibitor (Praluent® [alirocumab] or Repatha® [evolocumab]) at Week -2 (Visit S1) or prior use of a PCSK9 inhibitor within the past 4 weeks of Week -2 (Visit S1) will be excluded from this study.*

*Note: Patients are allowed to initiate a PCSK9 inhibitor as adjunctive therapy at Week 24 if the LDL-C threshold criteria have been met as described in Section 11.1.6.3.5.*

6. Recent (within 3 months prior to the screening visit [Week -2 (Visit S1)] or between screening and randomization visits) MI, unstable angina leading to hospitalization, uncontrolled, symptomatic cardiac arrhythmia (or medication for an arrhythmia that was started or dose changed within 3 months of screening), CABG, PCI, carotid surgery or stenting, cerebrovascular accident, transient ischemic attack (TIA), endovascular procedure or surgical intervention for peripheral vascular disease or plans to undergo a major surgical or interventional procedure (eg, PCI, CABG, carotid or peripheral revascularization). Patients with implantable pacemakers or automatic implantable cardioverter defibrillators may be considered if deemed by the Investigator to be stable for the previous 3 months.
7. Uncontrolled hypertension, defined as sitting systolic blood pressure (SBP)  $\geq 160 \text{ mmHg}$  and diastolic blood pressure (DBP)  $\geq 100 \text{ mmHg}$  after sitting quietly for 5 minutes. Note: If the initial blood pressure (BP) values meet or exceed the specified level, an additional BP assessment may be completed. If the systolic or the diastolic values continue to meet or exceed the threshold, the patient may not continue screening. However, at the discretion of the Investigator, the screening period may be extended up to 2 weeks to allow for a repeat qualifying BP assessment following adjustment of BP medication(s), provided that the patient has been on a stable dose of the BP medication for a minimum of 2 weeks prior to randomization and the repeat BP measurements do not meet the exclusion criteria
8. Hemoglobin A1C (HbA1C)  $\geq 10\%$  at Week -2 (Visit S1)
9. Uncontrolled hypothyroidism, including thyroid-stimulating hormone (TSH)  $>1.5 \times$  the upper limit of normal (ULN) at Week -2 (Visit S1). Patients stabilized on thyroid replacement therapy for at least 6 weeks prior to randomization are allowed.

10. Liver disease or dysfunction, including:

- Positive serology for hepatitis B surface antigen (HBsAg) and/or hepatitis C antibodies (HCV-AB) at Week -2 (Visit S1); or
- Alanine aminotransferase (ALT), aspartate aminotransferase (AST)  $\geq 2 \times$  ULN, and/or total bilirubin (TB)  $\geq 1.2 \times$  ULN at Week -2 (Visit S1).

*Note: If HCV-AB is positive, a reflex HCV RNA will be performed to rule out active disease. Patients without active disease may be enrolled in the study.*

Note: At the discretion of the investigator, the screening period may be extended up to 2 weeks for a single repeat of ALT, AST, and/or TB. For those patients who have a repeat ALT, AST, and/or TB, the repeat value will be used to determine eligibility.

*If TB  $\geq 1.2 \times$  ULN, a reflex indirect (unconjugated) bilirubin will be obtained and if consistent with Gilbert's disease, the patient may be enrolled in the study.*

11. Gastrointestinal conditions or procedures (including weight loss surgery; eg, Lap-Band® or gastric bypass) that may affect drug absorption
12. Hematologic or coagulation disorders or a hemoglobin (Hgb) level  $< 10.0$  g/dL (100 g/L) at Week -2 (Visit S1)
13. Active malignancy, including those requiring surgery, chemotherapy, and/or radiation in the past 5 years. *Patients with a history of nonmetastatic basal or squamous cell carcinoma of the skin and cervical carcinoma in situ are allowed*
14. Unexplained creatine kinase (CK)  $> 3 \times$  ULN at screening up to randomization (ie, not associated with recent trauma or physically strenuous activity). Patients with an explained CK elevation must have single repeat CK  $\leq 3 \times$  ULN prior to randomization.
15. History within the last 2 years of drug, alcohol, amphetamine and derivatives, or cocaine abuse. Patients with amphetamine derivatives prescribed by and under the care of a health care practitioner can be enrolled after evaluation by the Investigator.
16. Blood donation, *blood transfusion for any reason*, participation in a clinical study with multiple blood draws, major trauma, or surgery with or without blood loss within 30 days prior to randomization
17. Use of any experimental or investigational drugs within 30 days prior to screening or 5 half-lives, whichever is longer
18. Prior participation in a previous ETC-1002 clinical study. Prior participation in a clinical study with ETC-1002 is defined as having been enrolled in an ETC-1002 study.
19. Use of any of the following drugs within 3 months prior to screening or a plan to use these drugs during the study;
  - New or planned dose changes of systemic corticosteroids
  - Requirement for mipomersen or lomitapide or apheresis therapy

20. Planned initiation of the following drugs during the clinical trial or changes to the following drugs prior to randomization:
  - Hormone replacement (6 weeks prior to randomization)
  - Thyroid replacement (6 weeks prior to randomization)
  - Diabetes medications (4 weeks prior to randomization)
  - Obesity medication (3 months prior to randomization)
21. An employee or contractor of the facility conducting the study, or a family member of the Principal Investigator, Co-Investigator, or Sponsor.

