Study Hypothesis: The primary clinical hypothesis is that long-term exposure of ETC-1002 will be safe and well tolerated in high CV risk patients with hyperlipidemia (patients with underlying HeFH and/or ASCVD) who are not adequately controlled with their maximally tolerated lipid-modifying therapy, including a maximally tolerated statin. The study will characterize the long-term safety and tolerability of ETC-1002 versus placebo in addition to maximally tolerated lipid-lowering therapy, including a maximally tolerated statin, in patients with hyperlipidemia. The randomized, double-blind, placebo controlled add-on to maximally tolerated lipid-lowering therapy design will ensure that long-term safety data are meaningful and interpretable. The extended treatment duration (52 weeks) and large patient number (n = 1950) will provide robust long-term safety in high CV risk patients who have an unmet medical need for additional lipid-lowering therapy, such as ETC-1002 once daily, orally bioavailable option.

Methodology:

1002-040 STUDY DESIGN

ASCVD=atherosclerotic cardiovascular disease; HeFH=Heterozygous Familial Hypercholesterolemia

Study Design:

This is a Phase 3, randomized, double-blind, placebo-controlled, parallel group, study evaluating the long-term safety and tolerability of ETC-1002 in high CV risk patients with hyperlipidemia (patients with underlying HeFH and/or ASCVD) who are not adequately treated with their maximally tolerated lipid-modifying therapy. Maximally tolerated lipid-lowering therapy includes a maximally tolerated statin alone or in combination with other lipid-lowering therapies (eg, ezetimibe, fibrates [except gemfibrozil]). A patient's maximally tolerated lipid-modifying therapy will be determined by the investigator using their medical judgment and available sources, including the patient's self-reported history of lipid-modifying therapy. However, patients *who are currently taking simvastatin at average daily doses that are greater than 40 mg per day or who are currently taking a proprotein convertase subtilisin/kexin type 9 (PCSK9) inhibitor (alirocumab or evolocumab), or have taken a PCSK9 inhibitor within the past 4 weeks of Week -2 (Visit S1)* will be excluded from enrolling in this study. *PCSK9 inhibitors may be initiated as adjunctive therapy at Week 24 if the LDL-C threshold criteria have been met as described in Section 11.1.6.3.5.*

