  - Coronary revascularization procedure (eg, percutaneous coronary intervention [PCI] or coronary artery bypass graft [CABG] surgery)
  - Clinically significant CHD diagnosed by invasive or non-invasive testing (such as coronary angiography, stress test using treadmill, stress echocardiography, or nuclear imaging)
- Documented CHD risk equivalents (includes 1 or more of the following criteria):
  - Peripheral arterial disease
  - Previous ischemic stroke with a focal ischemic neurological deficit that persisted more than 24 hours, considered as being of atherosclerotic origin. Computed tomography (CT) or magnetic resonance imaging (MRI) must have been performed to rule out hemorrhage and non-ischemic neurological disease
- Be on maximally tolerated lipid-modifying therapy, including a *maximally tolerated statin either alone or in combination with other lipid-lowering therapies*, at stable doses and regimens for at least 4 weeks prior to screening (6 weeks for fibrates; *however, gemfibrozil is not allowed*). Regimens other than daily dosing, including those at very low doses, are acceptable.  
A patient's maximally tolerated lipid-modifying therapy will be determined by the investigator using their medical judgment and available sources, including the patient's self-reported history of lipid-modifying therapy.  
Patients currently taking *an average daily dose of simvastatin that is greater than 40 mg* will be excluded from this study.  
*Patients who are currently taking a PCSK9 inhibitor (Praluent® [alirocumab] or Repatha® [evolocumab]) or have taken a PCSK9 inhibitor within the past 4 weeks of Week -2 (Visit S1) will be excluded from this study.*

Exclusion Criteria:

- *Total fasting triglyceride ≥500 mg/dL (5.6 mmol/L) at Week -2 (Visit S1)*  
*Note: TG may be repeated 1 time with the screening period extended up to 2 weeks. For those patients who have a repeat TG, the mean of the first value and the repeat value will be used to determine eligibility.*
- *Renal dysfunction or nephritic syndrome or a history of nephritis, including eGFR (using central laboratory determined Modification of Diet in Renal Disease [MDRD] formula) <30 mL/min/1.73 m² at Week -2 (Visit S1) [1].*  
*Note: At the discretion of the investigator, the screening period may be extended up to 2 weeks for a single repeat eGFR. For those patients who have a repeat eGFR, the repeat value will be used to determine eligibility.*  

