*Note: Also excluded are renally impaired patients receiving an average daily dose of simvastatin 40 mg with eGFR below <45 mL/min/1.73 m².*
- *Body mass index (BMI) ≥50 kg/m²*
- *Concomitant use of simvastatin at average daily doses greater than 40 mg.*
- *Concomitant use of a PCSK9 inhibitor (Praluent® [alirocumab] or Repatha® [evolocumab]) at Week -2 (Visit S1) or prior use of a PCSK9 inhibitor within the past 4 weeks of Week -2 (Visit S1) will be excluded from this study.*  
*Note: Patients are allowed to initiate a PCSK9 inhibitor as adjunctive therapy at Week 24 if the*

*LDL-C threshold criteria have been met as described in Section 11.1.6.3.5.*

- Recent (within 3 months prior to the screening visit [Week -2 (Visit S1)] or between screening and randomization visits) MI, unstable angina leading to hospitalization, uncontrolled, symptomatic cardiac arrhythmia (or medication for an arrhythmia that was started or dose changed within 3 months of screening), CABG, PCI, carotid surgery or stenting, cerebrovascular accident, transient ischemic attack (TIA), endovascular procedure or surgical intervention for peripheral vascular disease or plans to undergo a major surgical or interventional procedure (eg, PCI, CABG, carotid or peripheral revascularization). Patients with implantable pacemakers or automatic implantable cardioverter defibrillators may be considered if deemed by the Investigator to be stable for the previous 3 months.
- Uncontrolled hypertension, defined as sitting systolic blood pressure (SBP)  $\geq 160$  mmHg and diastolic blood pressure (DBP)  $\geq 100$  mmHg after sitting quietly for 5 minutes. Note: If the initial blood pressure (BP) values meet or exceed the specified level, an additional BP assessment may be completed. If the systolic or the diastolic values continue to meet or exceed the threshold, the patient may not continue screening. However, at the discretion of the Investigator, the screening period may be extended up to 2 weeks to allow for a repeat qualifying BP assessment following adjustment of BP medication(s), provided that the patient has been on a stable dose of the BP medication for a minimum of 2 weeks prior to randomization and the repeat BP measurements do not meet the exclusion criteria
- Hemoglobin A1C (HbA1C)  $\geq 10\%$  at Week -2 (Visit S1)

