### **8.2.2. Prohibited Medications**

Patients will not have used medications (monotherapies or combination therapies) listed below within 4 weeks prior to screening or use these drugs during the study:

- New or planned dose changes of systemic corticosteroids. Stable doses of systemic corticosteroids at screening are allowed ( $\geq 4$  weeks). Short-term intermittent use ( $< 14$  days) of pulse steroids are allowed.
- Gemfibrozil (Lopid®)
- Cholestin (red yeast rice, also known as monascus purpureus extract)
- Simvastatin (Zocor®), *greater than or equal to 40 mg/day*
- *Ezetimibe/simvastatin where simvastatin doses are greater than or equal to 40 mg/day (Vytorin® 10 mg/40 mg and 10 mg/80 mg per day and Inegy® 10 mg/40 mg and 10 mg/80 mg per day are prohibited)*

*Patients will not have used the medications listed below within 4 weeks prior to screening:*

- Alirocumab (Praluent®)
- Evolocumab (Repatha®)
- *Note: Patients may be allowed to initiate a PCSK9 inhibitor as adjunctive therapy at Week 24 if the LDL-C threshold has been met as described in Section 11.1.6.3.5.*

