#### 10.2.1. Screening Week -2 (Visit S1; Days -16 to -4)

The screening period will begin with a screening visit that will occur 2 weeks prior to randomization. Visit S1 will allow the Investigator to assess the patient's preliminary eligibility. After the patient provides written informed consent (see Section 10.1), the patient will undergo the following assessments and procedures at Visit S1:

- Demographics
- Clinically relevant medical history, including assessment of HeFH status and ASCVD
- Concomitant and prohibited medication review
- Height (cm), weight (kg), BMI
- Vital signs
- Clinical laboratory evaluations:
  - Hematology, blood chemistry, coagulation, and urinalysis
  - Basic fasting lipids (TC, calculated LDL-C, HDL-C, non-HDL-C, and TG)
  - HbA1C
  - TSH
  - *FSH (in appropriate female patients)*
  - Serum pregnancy test (on appropriate female patients)

- Serology (including HBsAg, HCV)
- Review of all inclusion/exclusion criteria that can be assessed at this time
- Conduct diet and exercise counseling
- Contact IWRS to register the patient

Patients who meet all enrollment criteria that can be assessed at Visit S1 will be instructed to continue their therapy(s) for lipid regulation and to maintain consistent diet and exercise patterns throughout the study. Patients who fail to meet any entry criterion that can be assessed at Visit S1 are considered to be screen failures and are not required to return for additional visits (although a patient can be seen at any time for safety reasons).

Note:

- An optional visit approximately 1 week later MAY be completed if patient fails to meet a lipid entry criterion. If this optional visit is completed, the mean of lipid values from both visits will be used to determine eligibility.
- *An optional visit between Visits S1 and T1 may be scheduled to collect screening fasting labs in the event that the patient arrives at Visit S1 in a nonfasted state.*
- An optional visit between Visits S1 and T1 may be completed if the patient's DBP and/or SBP meet the exclusion criteria levels. Patients may randomize after blood pressure medications have been adjusted, they have been on stable doses of blood pressure medications for at least 2 weeks, and the repeat blood pressure values (DBP and/or SBP) no longer meet exclusionary values.

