#### **10.2.2. Treatment Week 0 (Visit T1; Day 1)**

Prior to scheduling Visit T1, review the screening clinical results to evaluate whether the patient continues to meet eligibility criteria.

- If the patient meets eligibility criteria, then schedule the Visit T1 and proceed with the Visit T1 procedures

If the patient has met all inclusion criteria and none of the exclusion criteria, the patient may be randomized into the double-blind treatment period. Patients who fail to meet any entry criterion prior to randomization are considered to be screen failures, will not be randomized into a treatment group, and are not required to return for additional visits. Patients are considered randomized once all eligibility criteria are confirmed and a randomization number is obtained by the IWRS on the day of first dose.

The patient will undergo the following assessments and procedures at (Visit T1)

- Concomitant and prohibited medication review (ongoing)
- Assess AEs (starting from signing of the informed consent document)
- Physical examination (PE)
- Weight
- 12-Lead electrocardiogram (ECG)
- Vital signs
- Clinical laboratory evaluations:
  - Hematology, blood chemistry, and urinalysis

*Note: Urine pregnancy test (for females of childbearing potential)*

- Basic fasting lipids (TC, calculated LDL-C, HDL-C, non-HDL-C, and TG)
- apoB
- HbA1C
- hs-CRP
- Reserve sample
- *Genetic sample (if the patient has consented to provide a genetic sample)*

- Review inclusion/exclusion criteria to establish patient eligibility
- Conduct diet and exercise counseling
- IWRS contact to obtain the patient randomization number and MED ID number for double-blind study drug
- Dispense IMP and provide dosing instructions
- Schedule next visit

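### Section 7.2 and the synopsis still exclude only simvastatin above 40 mg/day, while the rest of the current plan bars 40 mg/day or more

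*Protocol*

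**What the plan says.** The current protocol gives two different simvastatin limits.

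Limit above 40 mg/day:
- Section 7.2, criterion 4: concomitant simvastatin "at average daily doses greater than 40 mg".
- Synopsis, Study Design: patients "who are currently taking simvastatin at average daily doses that are greater than 40 mg per day" are kept out.
- Synopsis, inclusion list: the bar is on "an average daily dose of simvastatin that is greater than 40 mg".
- Synopsis, exclusion list: "Concomitant use of simvastatin at average daily doses greater than 40 mg".
- Note to the renal criterion, in both 7.2 (criterion 2) and the synopsis: "Also excluded are renally impaired patients receiving an average daily dose of simvastatin 40 mg with eGFR below" 45 mL/min/1.73 m².

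Limit at 40 mg/day or more:
- Section 8.2.2 prohibits plain simvastatin from 40 mg/day upward and, for the fixed combination, "Ezetimibe/simvastatin where simvastatin doses are greater than or equal to 40 mg/day". The ban runs from 4 weeks before screening and through the study.
- Section 8.2.1 allows simvastatin, alone or with ezetimibe, only below 40 mg.
- The footnote to protocol Table 3, and the footnotes to Tables 1 and 2 in SAP section 4.2, do not allow 40 mg/day or more.
- The rescue rule for raised LDL-C (synopsis and section 11.1.6.3.5) rules out 40 mg/day or more as a treatment change. A later sentence in the same list still tells patients who reach simvastatin 40 mg through a treatment change to attend the extra safety visits.

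**The concern.** Eligibility is decided on the criteria lists. Section 10.2.2 states: "If the patient has met all inclusion criteria and none of the exclusion criteria, the patient may be randomized into the double-blind treatment period". A site that works from 7.2 would find no simvastatin reason to refuse a patient on exactly 40 mg/day whose eGFR is 45 or more. A site that works from 8.2.2 would have to refuse the same patient.

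The limit concerns safety. Amendment 4 added the renal note and the extra visits for patients on 40 mg at the FDA's request. Item 10 of the SAP's summary of changes says that under Amendment 5 patients on 40 mg/day or more were taken off study treatment. Eligibility text that still admits the dose works against that decision. The rescue sentence raises a similar doubt for patients already in the study, because it can be read as treating 40 mg as a permitted rescue dose.

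**Working it through.** There is no power or sample-size figure to reproduce. The check sets the passages side by side.

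**1. Where the rules disagree.** The 7.2 column applies the criterion 2 note and criterion 4.

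| Average daily simvastatin | eGFR | Section 7.2 | Section 8.2.2 |
|---|---|---|---|
| Below 40 mg | 30 or more | not excluded | not barred |
| Exactly 40 mg | below 45 | excluded by the note | barred |
| Exactly 40 mg | 45 or more | **not excluded** | **barred** |
| Above 40 mg | any | excluded by criterion 4 | barred |

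The only conflict is in the third row. The note shows that the gap follows from the text as it stands: a separate exclusion of 40 mg at low eGFR has a purpose only if 40 mg is otherwise acceptable.

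**2. Count.** Limits set above 40 mg: 1 in section 7.2 + 3 in the synopsis = 4. Copies of the renal note: 1 in section 7.2 + 1 in the synopsis = 2. Total: 4 + 2 = 6 statements. One of the six, in the synopsis Study Design paragraph, is narrative and not a listed criterion. The rescue sentence adds two copies.

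**3. How the mismatch arose.** The change logs serve here only as history; the conflict itself lies within the current text. Before Amendment 3, daily simvastatin 40 mg was excluded. Amendment 3 moved the limit to above 40 mg and edited the synopsis eligibility text, 7.2, 8.2.1 and 8.2.2 together. Amendment 4 added the renal note. Amendment 5 has five changes headed as adding simvastatin 40 mg to the prohibited medications (Changes 3, 6, 7, 8 and 13). Their locations are the synopsis safety-monitoring text, Tables 2 and 3, 8.2.1, 8.2.2 and 11.1.6.3.5. None of the 5 lists 7.2 or the synopsis eligibility text.

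**4. Could it still affect enrolment?** Section 6.4 plans about 28 months from first visit to last visit, and section 6.3 plans about 54 weeks per patient. 54 × 7 / 30.4 ≈ 12.4 months, and 28 − 12.4 ≈ 15.6 months for screening. The first-visit date is not given. Counting back 15.6 months from Amendment 5 (10 May 2017) gives late January 2016. On the planned timeline, an earlier first visit means that screening had closed by Amendment 5, and a later one means that it was still open. The documents do not settle which.

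**5. What an unqualified edit would do.** SAP section 5.2.2 judges entry deviations against the protocol's criteria without naming a version, and the SAP introduction refers to Amendment 5. Patients on exactly 40 mg could enter validly under Amendment 3, and under Amendment 4 if eGFR was 45 or more. Replacing the limit outright would make these patients look like entry deviations.

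**The case against.** The strongest reply is that the plan already blocks such a patient. Section 8.2.2 applies from 4 weeks before screening. "Concomitant and prohibited medication review" is required at Visit S1 and again at T1, when the patient is randomized. Section 6.6.1 refers to section 8.2 when it describes eligible patients' concomitant medication. Section 10.2.2 says only that a patient may be randomized. A specific ban would also normally prevail over a looser criterion.

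Much of this stands. The medication review is a real safeguard and should work if sites apply 8.2.2. It is partial, though. Section 6.6.1 ties only the stability of regimens to section 8.2, and no criterion in 7.2 refers to the prohibited list.

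Two further points limit what can be said. First, a reader might infer from the Amendment 5 log that the omission is a proven oversight. The pattern fits one, but the first bullet of that amendment's justification is blacked out, so the reason is unknown. The blacked-out bullet cannot be presumed to justify the mismatch either. Second, a reader might conclude that the renal note and the rescue sentence are dead text to be deleted. The documents do not support that. The note was an entry criterion under Amendment 4. The Amendment 5 justification keeps the extra visits for consenting patients who had been on 40 mg or more and were taken off study drug, and a patient moved to 40 mg as rescue before Amendment 5 could belong to that group.

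**Conclusion.** The concern holds as an inconsistency in a stated safety limit: the eligibility text is wrong at exactly 40 mg/day with eGFR 45 or more. Six statements are affected, along with a rescue sentence that is ambiguous in two places. It should be fixed, because the threshold is a safety limit and the correction is cheap.

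Its practical effect is unknown. It depends on whether screening was still open at Amendment 5 and on whether sites applied 8.2.2 during medication review. If screening had closed, the eligibility edit only sets the record straight, and the rescue sentence is what remains to clarify for patients still in the study.

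A reader might infer that patients on a banned dose were enrolled because of this text. The documents give no count of patients on 40 mg/day and show no such case; those withdrawn under Amendment 5 could have entered validly under Amendments 3 and 4. Nor is there an effect on power, alpha or endpoints. The SAP summaries of patients on 40 mg or more select patients by statin use at any time during the study, so they do not depend on the eligibility wording.

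**What to change.** 1. In section 7.2 criterion 4 and the three synopsis statements, say that simvastatin at 40 mg/day or more is excluded for patients randomized under Amendment 5 or later.
2. Keep the above-40 mg limit only as the criterion for patients randomized under Amendments 3 and 4, and keep the 40 mg with eGFR below 45 note only for those randomized while it was in force. The deviation review in SAP section 5.2.2 then uses the version that applied at each patient's entry.
3. In the synopsis rescue text and section 11.1.6.3.5, limit the simvastatin 40 mg sentence to patients moved to that dose before Amendment 5 who are now off study drug and in safety follow-up. It then no longer suggests that 40 mg is an allowed rescue dose.

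The cost is a wording correction by amendment or clarification letter. It needs no extra patients, visits or analyses.
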